5.3 Agent Administration

All participants will be instructed to swallow the double-blinded medications in the morning with food.

Monitoring and Intervention Phases: Visit Breakdown – Refer to study calendar in section 9.

Monitoring Phase (duration: 1-10 weeks):

- Visit 1: Collection of baseline data.
 - a. Patient demographic information and clinical characteristics will be collected by self-administered surveys.

- b. Completion of self-reported fatigue, anxiety, depression, sleep and quality of life questionnaires.
- Visits 2-10 (in person or by phone): Monitoring procedures including completion of self-reported fatigue and other quality of life questionnaires

The occasional mis-timed (or missed) FACIT does not automatically constitute a protocol violation. However, in order to remain in compliance with the protocol, a minimum of 4 FACITs is needed for partial breast irradiation patients, 5 FACITs for hypofractionation patients, and 7 FACITs for standard (6 week) fractionation patients. The monitoring phase terminates either at entrance into the intervention phase of the study, or at 4 weeks after the conclusion of radiation therapy, whichever comes first.

Intervention Phase (duration 5 weeks):

- Visit 1a:
 - a. consent for trial;
 - b. review of concomitant medications;
 - c. complete baseline fatigue questionnaire (unless completed within past week)—may be completed at Visit 1b;
 - d. complete anxiety, depression, sleep and quality of life questionnaires (unless completed within past week)—may be completed at Visit 1b;
 - e. urine HCG only in women with reproductive potential; blood draw to evaluate LFTs, Hct, BUN/Cr unless results are available within the previous month;
 - f. specimens will be banked for future analysis of fatigue-related genetic polymorphisms and inflammatory biomarkers (participants can opt out of specimen banking)
- Visit 1b: laboratory study results reviewed to confirm eligibility; receive medication bottles and medication diary; receive patient education sheet on contraindicated medications and safety card (see Appendix A); Visit 2 (one week after starting study drug vs. placebo): fatigue/response and adverse event assessment for dose escalation, review of concomitant medications, fatigue assessment

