- Visit 3 (five weeks after initiating study drug vs placebo): complete follow-up fatigue, anxiety, depression, sleep and quality of life questionnaires; review of concomitant medications; return medication bottles and diaries. Blood draw for LFTs.

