5.7 Criteria for Removal from Study

1. Initiation of opioid therapy, or newly expected need for opioid therapy while on study drug

2. Emergence of suicidal ideation
3. Moderate or severe hepatic impairment (AST and ALT > 3x ULN; Bilirubin > 1.5 ULN)
4. Moderate or severe renal impairment (Creatinine > 1.5x ULN)
5. Clinically significant respiratory or cardiac disease
6. Significant deviation from study protocol
7. Need to hold drug for more than 3 days, for any reason

Participants will be removed from the study when any of the criteria listed in Section 5.7 applies. The reason for study removal and the date the participant was removed must be documented in the case report form (CRF). Alternative care options will be discussed with the participant.

A QACT Treatment Ended/Off Study Form should be filled out when a participant completes study treatment and again when the participant comes off study. This form can be found on the QACT website or obtained from the QACT registration staff.

[figure not shown]
In the event of unusual or life-threatening complications, investigators must notify the Overall PI, [name], at [contact], [name] or via email ([contact]) within 24 hours of discovery.

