Psychiatric emergencies: Suicidal ideation is a rare (<=1%) adverse event associated with naltrexone use in individuals receiving IM naltrexone for alcohol and opioid dependence but it was not observed in those treated with naltrexone orally or in those receiving it for other indications (i.e., obesity, smoking cessation, binge eating disorder). Suicidal ideation will be assessed during the trial each time the PHQ-9 depression self-report questionnaire is completed. The CRC will be scoring the PHQ9 and if the score is greater than or equal to 10, the CRC will notify the participant’s Radiation Oncologist as well as the study’s psychiatrist so that they can discuss with the participant the options for clinical follow-up and further care. Suicidal ideation that is indicated on the PHQ-9 or spontaneously reported will constitute a serious adverse event. This evaluation will be conducted by one of the study clinicians with psychiatric expertise and/or by mental health staff in the MGH or BWH emergency rooms, if appropriate. These participants will be followed by study psychiatrists until a local mental health clinician is available for ongoing treatment. Study medication will be discontinued in any participant who develops suicidal ideation. The following established algorithm will be employed:

Specific Algorithms for Addressing Participant Reports of Suicidal Ideation

Algorithm based on response to PHQ-9:				Algorithm based on participant volunteering possible suicidal ideation	
ITEM 13.9: Over the last 2 weeks, how often have you been bothered by				Ask: Have you had thoughts of actually hurting yourself?	
.... Thoughts that you would be better off dead or of hurting yourself in some way?					
If participant responds (shaded areas)				If participant responds (shaded area)	
Not at all	Several days	More than half the days	Nearly every day	NO	YES
0	1	2	3		

 
Ask: Have you had thoughts of actually hurting yourself? If participant responds (shaded area) NO YES
 
Ask three screening questions about plan, probability and preventing factors:
	
Shaded response requires one of the following to be done the same day:
 
 • Refer participant to study psychiatrist • Send participant to an emergency room, or • Send participant to another mental health professional

Plan: 1. Have you thought about how you might actually hurt yourself? NO YES [ask HOW?]
	

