6.1 Expected Toxicities

Safety Profile

Gastrointestinal side effects of oral naltrexone (10-33%) include gastrointestinal symptoms such as nausea ($\geq 10\%$), vomiting ($\geq 3\%$), anorexia ($< 10\%$), constipation ($< 10\%$), and diarrhea ($< 10\%$). During controlled trials of oral naltrexone in alcohol dependence, approximately 5% of patients discontinued the drug because of nausea. CNS side effects of oral naltrexone include headache ($\geq 7\%$), dizziness (4—9%), nervousness ($\geq 4\%$), insomnia ($\geq 3\%$), anxiety ($\geq 2\%$), fatigue ($\geq 4\%$), drowsiness ($\leq 2\%$), increased energy ($< 10\%$), irritability ($< 10\%$), paranoia ($< 1\%$), restlessness ($< 1\%$), confusion ($< 1\%$), disorientation ($< 1\%$), hallucinations ($< 1\%$), nightmares ($< 1\%$), yawning ($< 1\%$), and hot flashes ($< 1\%$). Miscellaneous side effects include rash ($< 10\%$), increased thirst ($< 10\%$), and chills ($< 10\%$). Serious side effects of naltrexone ($< 1\%$) include hepatotoxicity (only reported at doses of 300mg/day or higher) and eosinophilic pneumonia (only reported with depot administration of naltrexone).

In controlled clinical trials of the extended-release injectable suspension of naltrexone, suicidal ideation, suicide attempts, or completed suicides occurred in 1% of patients and in no patients treated with placebo. In some cases, the suicidal thoughts or behavior occurred after study discontinuation but were in the context of an episode of depression that began while the patient was taking naltrexone. Although the incidence of adverse psychiatric events is expected to be considerably lower in the present study population as compared to populations of patients with alcohol and opioid dependence, depression and suicidal ideation will be systematically monitored during the present study using standardized self-report instruments.

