6.1.1 Adverse Events List(s)
Adverse Event List(s) for naltrexone

Common (10-33%)	Uncommon (1-10%)	Serious (<1%)
Nausea	Vomiting Anorexia Diarrhea	Elevated liver function tests Suicidal ideation

	Constipation Rash Headache Dizziness Nervousness Insomnia Anxiety Irritability Increased thirst	
--	---	--

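### The rule to stop study drug for suicidal ideation has no scheduled PHQ-9 behind it until week 5, when the drug is handed back

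*Combined protocol and SAP*

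**What the plan says.** Section 5.7 lists "Emergence of suicidal ideation" among the removal criteria and adds, under psychiatric emergencies: "Study medication will be discontinued in any participant who develops suicidal ideation". The same text gives the means of assessment: "Suicidal ideation will be assessed during the trial each time the PHQ-9 depression self-report questionnaire is completed". Ideation that a participant volunteers is also handled, through its own algorithm.

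Section 6.1 undertakes that "depression and suicidal ideation will be systematically monitored during the present study using standardized self-report instruments", without giving a frequency. In the table in Section 6.1.1, the column for serious events below 1% reads "Elevated liver function tests Suicidal ideation".

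The intervention calendar in Section 9 marks the PHQ-9 at week 0 and week 5; weeks 1 and 9 are blank. Section 5.3 agrees. Visit 2 (week 1) covers fatigue, adverse events and concomitant medications. Visit 3 (week 5) includes the depression questionnaire, and at that visit participants "return medication bottles and diaries".

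The PHQ-9s of the monitoring phase do not carry over: "The monitoring phase terminates either at entrance into the intervention phase of the study".

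On the liver, Section 6.1 requires LFTs one week after starting study drug for participants taking more than 800 mg of ibuprofen daily or the equivalent. Neither Visit 2 in Section 5.3 nor the week-1 column of the calendar shows that test.

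**The concern.** A stopping rule can shorten exposure only if its trigger can be observed while drug is being taken. Here the one instrument named for assessing ideation is first used after dosing has begun at the visit where dosing ends. The week-1 visit exists, according to Section 1.1, to rule out contraindications to raising the dose from 25 mg to 50 mg, and Section 5.8 gives a study psychiatrist a part in that decision. No PHQ-9 is scheduled to inform it.

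What is at stake is participant safety at low frequency. No efficacy result is affected. A positive answer at week 5 would still lead to psychiatric evaluation and follow-up, but it would come too late for the discontinuation rule to change exposure.

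**Working it through.** **Inputs.** Treatment lasts 5 weeks, or 35 days (5.5). Intervention visits have a window of 7 days either way (1.1). The PHQ-9 asks about the last 2 weeks (appendix form). PHQ-9 visits are at weeks 0 and 5 (9). There are 150 patients per arm (12.2). The PHQ-9 takes 3 minutes (10.1) and the week-1 visit is planned at 15 minutes (9). The plan gives no figure of its own to reproduce.

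**Convention.** The first dose is on day 1, and the nominal visits are on days 7 and 35. A PHQ-9 on day d covers days d-13 to d.

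**Coverage as planned.**
- Visit on day 35: covers days 22-35 and leaves days 1-21 uncovered, 21/35 = 60%.
- Visit on day 28: leaves days 1-14 (14 days).
- Visit on day 42: leaves days 1-28 (28 days).
- PHQ-9s scheduled after the first dose and before the visit at which drug is returned: 0.

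**Coverage with a week-1 PHQ-9.** Let that visit fall on day w, from 1 to 14.
- Since w-13 is at most 1, every dosing day up to the visit is covered.
- The remaining gap runs from day w+1 to day d-14. For w=7 and d=35 it is days 8-21, or 14 days. For w=14 and d=28 it is 0 days. For w=1 and d=42 it is days 2-28, or 27 days.
- For onset on days 1-7, the nominal wait to the first scheduled PHQ-9 falls from 28-34 days (35-7 to 35-1) to 0-6 days (7-7 to 7-1).

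**Expected frequency.** Section 5.7 says of ideation that "it was not observed in those treated with naltrexone orally", which gives 0 cases. Section 6.1 gives 1% for suicidal ideation, attempts or completed suicides with the injectable form: 150 x 0.01 = 1.5, unadjusted for exposure. Section 2.2 gives 12-52 weeks for most placebo-controlled dependence trials. If those durations apply to the 1% figure and the hazard is constant (both assumptions):
- five weeks: 1.5 x 5/52 = 0.14 to 1.5 x 5/12 = 0.63 cases;
- days 1-7 only: 1.5/52 = 0.03 to 1.5/12 = 0.13 cases.

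**Liver test.** If the week-1 test is missed, the next scheduled LFT is on day 35, 35-7 = 28 days later (21-35 with the week-5 window).

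**Cost.** 3/15 = 20% more time at one visit; 300 x 3 minutes = 900 minutes = 15 hours of participant time.

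**The case against.** **Other routes exist.** An adverse event assessment is scheduled at week 1, on a form meant for trials of psycho-active drugs and reviewed by the study psychiatrists (Section 6). A reader might infer that no ideation question of any kind is asked on drug. The documents do not support that. None of the 95 numbered SAFTEE lines reproduced asks about suicidal thoughts, but the reproduction looks incomplete. Five events expected in Section 6.1.1 (rash, nervousness, insomnia, anxiety, irritability) have no printed item, and the medication diary begins at day 18. Section 5.7 also says that ideation is assessed at each PHQ-9, not only then. What is established is that no PHQ-9 is scheduled.

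**The event is rare and participants are screened.** Section 3.4 excludes major depression and ideation. The entry questionnaires are at most about a week old (5.3). Section 6.1 expects adverse psychiatric events to be considerably less frequent than in dependence populations. This stands, and it limits the size of the point. A reader might take 1.5 cases as the expectation; that carries an injectable rate over to a short oral course.

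**No contradiction.** Section 6.1 promises systematic monitoring but sets no frequency, so the calendar does not breach it. That is correct. The weakness is that the schedule does not serve the stopping rule.

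**The remedy is partial.** A week-1 PHQ-9 covers the 25 mg week. The weeks at up to 50 mg still have none until drug return. This also stands, and the protocol should say so.

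**The liver omission is editorial.** Section 6.1 is clear and binding, concomitant medications are reviewed at weeks 0 and 1, and Section 5.4 places the NSAID effect above the therapeutic dose range. This is accepted.

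**Conclusion.** The point holds for the PHQ-9. No PHQ-9 falls between the first dose and the visit where drug is returned, and nominally 21 of 35 dosing days (14 to 28 days with the week-5 window) lie outside any PHQ-9's recall. This rests on the calendar and the visit list, which agree, and on taking the two-week recall literally.

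The expected number of participants affected is very small: none on the oral evidence cited in Section 5.7, and 0.14-0.63 under the exposure scaling above. That scaling is illustrative, because the documents do not give the duration of the trials behind the 1%. The case for change is that the protocol itself lists the event as serious and makes discontinuation mandatory, while a scheduled check before escalation costs little. It is a recommended safety improvement, with no bearing on the validity of the trial.

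A reader might infer from the calendar that heavy NSAID users have no week-1 liver test. The documents do not support that, since Section 6.1 requires it. Two places simply fail to repeat the requirement.

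**What to change.** 1. Add the PHQ-9 to the existing week-1 visit, in both Section 5.3 (Visit 2) and the Section 9 calendar, and require its review before the escalation decision.
2. State in Section 5.7 that about days 8-21, on the escalated dose, still rely on volunteered reports.
3. As an alignment edit, add the week-1 LFT for participants on more than 800 mg ibuprofen daily or equivalent to the Visit 2 text and as a footnote to the calendar. This adds no test beyond what Section 6.1 requires.

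The cost is a text and calendar amendment, about 3 minutes per participant (at most 15 hours over 300 participants), and no new visit. There will be some extra notifications for scores of 10 or more, because the tiredness, sleep and appetite items count and participants are selected for fatigue. At a maximum of 3 points each, those three items can supply 9 of the 10. A day-7 PHQ-9 also recalls about 7 days before the first dose, so a positive answer should be read against the week-0 form. Score thresholds and stopping rules do not change.

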5.8 DOSING DELAYS/DOSE MODIFICATIONS

Study drug will be increased to 50mg after 1 week of therapy unless fatigue has improved substantially on the lower dose or there are contraindications to this planned dose increase (including, but not limited to, adverse events grade II or higher that are thought to be related to study drug), as judged by the research nurse and study psychiatrist.

Some patients may tolerate the 25mg dose but develop toxicity after the dose is increased to 50mg. Hence, drug dose can be decreased from 50mg to 25mg in the setting of new-onset adverse events grade II or higher by CTCAE judged to be definitely or probably related to study drug.

Study drug (either at the 25mg or 50mg dose) can also be held for up to three days and then

restarted in setting of adverse events grade II or higher by CTCAE if these events are judged to be possible, unlikely or unrelated to study drug. If the drug must be held for more than three days, the participant will need to come off the study.

	Remain at 25 mg dose instead of increasing to 50 mg	Dose reduction to 25 mg dose after increasing to 50 mg dose	Dose hold at either 25 mg or 50 mg dose for up to 3 days
Conditions	
 Substantially reduced fatigue on 25 mg dose Adverse events grade II or higher determined by CTCAE guidelines Other conditions deemed significant by the research nurse and study psychiatrist 	
 New onset adverse events grade II or higher by CTCAE guidelines definitely or probably related to study drug Other conditions deemed significant by the research nurse and study psychiatrist 	
 Adverse events grade II or higher by CTCAE guidelines possibly, unlikely, or unrelated to study drug Other conditions deemed significant by the research nurse and study psychiatrist

6. ADVERSE EVENTS: LIST AND REPORTING REQUIREMENTS

Adverse event (AE) monitoring and reporting is a routine part of every clinical trial. The following list of reported and/or potential AEs (Section 6.1) and the characteristics of an observed AE (Section 6.2) will determine whether the event requires expedited reporting **in addition** to routine reporting.

Adverse events will be monitored explicitly using a standardized adverse event form used in trials for psycho-active medications that will be reviewed by the study psychiatrists.

6.1 Expected Toxicities

Safety Profile

Gastrointestinal side effects of oral naltrexone (10-33%) include gastrointestinal symptoms such as nausea ($\geq 10\%$), vomiting ($\geq 3\%$), anorexia ($< 10\%$), constipation ($< 10\%$), and diarrhea ($< 10\%$). During controlled trials of oral naltrexone in alcohol dependence, approximately 5% of patients discontinued the drug because of nausea. CNS side effects of oral naltrexone include headache ($\geq 7\%$), dizziness (4—9%), nervousness ($\geq 4\%$), insomnia ($\geq 3\%$), anxiety ($\geq 2\%$), fatigue ($\geq 4\%$), drowsiness ($\leq 2\%$), increased energy ($< 10\%$), irritability ($< 10\%$), paranoia ($< 1\%$), restlessness ($< 1\%$), confusion ($< 1\%$), disorientation ($< 1\%$), hallucinations ($< 1\%$), nightmares ($< 1\%$), yawning ($< 1\%$), and hot flashes ($< 1\%$). Miscellaneous side effects include rash ($< 10\%$), increased thirst ($< 10\%$), and chills ($< 10\%$). Serious side effects of naltrexone ($< 1\%$) include hepatotoxicity (only reported at doses of 300mg/day or higher) and eosinophilic pneumonia (only reported with depot administration of naltrexone).

In controlled clinical trials of the extended-release injectable suspension of naltrexone, suicidal ideation, suicide attempts, or completed suicides occurred in 1% of patients and in no patients treated with placebo. In some cases, the suicidal thoughts or behavior occurred after study discontinuation but were in the context of an episode of depression that began while the patient was taking naltrexone. Although the incidence of adverse psychiatric events is expected to be considerably lower in the present study population as compared to populations of patients with alcohol and opioid dependence, depression and suicidal ideation will be systematically monitored during the present study using standardized self-report instruments.

Naltrexone blocks the effects of opioid analgesics and should not be used in patients who are currently on opioid analgesia, who have received opioids within the past 7 days (14 days for longer-acting opioids such as methadone), or who are expected to require opioid analgesia within the next 7 days. If opioids are required, the patient should stop naltrexone and wait 3 days before initiating opioids. If necessary, reversal of opioid blockade before the 3-day time period is possible to achieve, but should be done only under medical supervision, as higher doses may be required to achieve effective analgesia creating a risk of respiratory depression. Such supervision should occur in medical settings with the provision for respiratory support. This would include a hospital emergency department or intensive care unit.

Potential study participants will be strongly cautioned about unpleasant side effects of opioid withdrawal that may occur if they are on opioids at the time study drug is initiated. In addition, medication lists in LMR will be reviewed by study staff to verify the participant’s self-report of opioid use.

Participants may use standard doses of acetaminophen, NSAIDs, or aspirin for analgesia during the study. Subjects on daily NSAIDs of >800mg ibuprofen daily (or the equivalent) will have LFTs one week after initiation of study drug. All participants will be instructed to report any symptoms of abdominal pain lasting more than a few days, white bowel movements, dark urine, or yellowing of their eyes. In the setting of these symptoms, liver function tests will be checked immediately.

Finally, if participants require opioid analgesia emergently during the course of the study, they will be taken off study. Study staff will notify the PI and QACT so that the treatment assignment (naltrexone or placebo) can be unblinded prior to initiating opioid analgesia. If the participant was assigned to naltrexone, the opioid analgesia will need to occur in a supervised medical setting, as above.

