6.2 Adverse Event Characteristics

Reporting of adverse events:

All toxicities or adverse events occurring between the start of treatment and 30 days following the end of treatment will be recorded and graded as to severity and relationship to study drug. Any toxicity that is moderate or serious will be immediately reported by phone or email to the PI within 24 hours of discovery. All serious adverse reactions will be reported to the PI who will then notify the IRB.

A **serious adverse reaction** is defined as any of the following: life threatening; permanently disabling; requiring inpatient hospitalization or prolonging or hospitalization; death while on study treatment

A **moderate adverse reaction** is defined as the following: discomfort severe enough to cause interference with usual activities; persistent or requiring treatment

A **mild adverse reaction** is defined as the following: awareness of signs/symptoms, but easily tolerated; are of minor irritant type; causing no loss of time from normal activities; symptoms would not require medication or a medical evaluation; signs/symptoms are transient in nature

Preexisting medical conditions and symptoms related to known underlying diseases will not be recorded as adverse events unless they significantly worsen in severity during the course of the study.

Other than possible drug side effects, participants may also experience inconvenience and/or emotional distress, due to filling out instruments focusing on physical and emotional symptoms.

In case of subject distress, study psychiatrists can be contacted.

- **CTCAE term (AE description) and grade:** The descriptions and grading scales found in the revised NCI Common Terminology Criteria for Adverse Events (CTCAE) version 4.0 will be utilized for AE reporting. All appropriate treatment areas should have access to a copy of the CTCAE version 4.0. A copy of the CTCAE version 4.0 can be downloaded from the CTEP web site http://ctep.cancer.gov/protocolDevelopment/electronic_applications/ctc.htm.
- **For expedited reporting purposes only:**
 - AEs for the agent(s) that are listed above should be reported only if the adverse event

varies in nature, intensity or frequency from the expected toxicity information which is provided.

- Other AEs for the protocol that do not require expedited reporting are outlined in the next section (Expedited Adverse Event Reporting) under the sub-heading of Protocol-Specific Expedited Adverse Event Reporting Exclusions.

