a. Clinical Variables form completed once at end of radiation treatment for every patient in monitoring phase

b. baseline questionnaires to be completed within ≤ 21 days prior to, or within 3 days of starting radiation therapy, otherwise they need to be repeated.

c. Complete once at baseline, once within one week after start of radiation, then once 4 weeks after completion of RT

d. Complete once at baseline, once within one week after start of radiation, then once while obtaining the final monitoring FACIT 4 weeks after end of RT

e. LFTs, BUN/Creatinine, Hematocrit will be accepted if drawn within 30 previous day; TSH within 6 months.

f. To be completed by study coordinator at time when patient is taken off-study for any reason. If patient continues on to Intervention Phase, this form will be completed when taken off intervention phase.

Study measures, type of procedure, and study visit schedule
Monitoring Phase (Hypofractionation Radiation)

	Type	Baseline Visit	Monitoring Visits	Meets Fatigue Eligibility Threshold
Background Information				
Consent		X		
Demographics/Patient Characteristics Form	Self-report	X		
Clinical Variables ^a			X ^a	
Fatigue				
FACIT-Fatigue Subscale	Self-report	X ^b	X ^c	X
PGI-F	Self-report	X ^b		
Sleep				
PSQI	Self-report	X ^b		
ISI	Self-report	X ^b		
ESS	Self-report	X ^b		
Berlin Questionnaire	Self-report	X ^b		
Other Target Symptoms				
GAD7	Self-report	X ^b		
PHQ9	Self-report	X ^b	X ^d	
FACT-B/FACT-ES	Self-report	X ^b	X ^d	
CPFQ	Self-report	X ^b		
PEG	Self-report	X ^b		
Safety monitoring				
Urine β -HCG				X
LFTs ^e				X
BUN/Creatinine ^e				X
Hematocrit ^e				X
TSH ^e				X
Subject Exit form (if applicable)				X ^f

a. Clinical Variables form completed once at end of radiation treatment for every patient in monitoring phase

b. baseline questionnaires to be completed within ≤ 21 days prior to, or within 3 days of starting radiation therapy, otherwise they need to be repeated.

c. Complete once at baseline, weekly during RT, then once 4 weeks after completion of RT

d. Complete once at baseline, once during the final week of RT, then once while obtaining the final monitoring FACIT 4 weeks after end of treatment

e. LFTs, BUN/Creatinine, Hematocrit will be accepted if drawn within 30 previous day; TSH within 6 months.

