f. To be completed by study coordinator at time when patient is taken off-study for any reason. If patient continues on to Intervention Phase, this form will be completed when taken off intervention phase.

Study measures, type of procedure, and study visit schedule
Intervention Phase

	Week 0 Randomi zation Visit	Week 1 Rx Visit (+/- 7 days)	Week 5 Rx Visit (+/- 7 days)	Week 9 Follow- up Visit (+/- 7 days)
Background Information				
Consent	X			
Fatigue				
FACIT-Fatigue Subscale	X	X	X	X
PGI-I	X		X	
Sleep				
PSQI	X		X	
ISI	X		X	
ESS	X		X	
Berlin Questionnaire			X	
Other Target Symptoms				
GAD7	X		X	
PHQ9	X		X	
FACT-B/FACT-ES	X		X	
CPFQ	X		X	
PEG	X		X	
Safety monitoring				
LFTs			X	
Concomitant medications	X	X	X	
Adverse Events assessment		X	X	
Health status/life events review				X
Dispense medication	X	X		
Review medication diary	X	X	X	
Study Summary				
Subject Exit form				X ^a
Study Visit duration (min)	40	15	40	15

a. To be completed by study coordinator at time when patient is taken off-study for any reason.

Effect measures listed in the Table of Procedures are described below. In addition to these effect measures, we will examine potential covariates that may play a role in the evolution of fatigue during breast radiotherapy. These include radiotherapy related characteristics such as breast volume; type of radiotherapy (e.g. fractionation schedule, number of fields, design of tangent fields [e.g. partial vs. full breast irradiation], boost dose [mini-tangents vs. electrons]. Exercise type/frequency and travel time to clinic will be assessed, as these parameters have correlated with radiotherapy-emergent fatigue in prior studies³⁹. Finally, hematocrit will be measured at baseline.

The related symptom measure of obstructive sleep apnea will be evaluated via the Berlin Questionnaire and Epworth Sleepiness Scale:

Berlin Questionnaire (BQ): (Time: 2 minutes) The BQ will be done once at the beginning of the

study. It is an instrument used to identify patients at high risk for sleep apnea based on symptoms related to snoring and daytime sleepiness along with the presence of hypertension or obesity. It has been found to have high sensitivity and specificity in a primary care setting.⁴⁰

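### No PHQ-9 and no adverse-event assessment is scheduled in the month after dosing, although the plan promises systematic mood monitoring and counts events to 30 days

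*Combined protocol and SAP*

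**What the plan says.** Section 6.1 describes controlled trials of the extended-release injection in which some suicidal thoughts or behaviour "occurred after study discontinuation but were in the context of an episode of depression that began while the patient was taking naltrexone". It expects far fewer psychiatric events in this population, but still commits that "depression and suicidal ideation will be systematically monitored during the present study using standardized self-report instruments". The table in Section 6.1.1 lists suicidal ideation as a serious event at under 1%.

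Section 5.7 says of ideation that "it was not observed in those treated with naltrexone orally or in those receiving it for other indications". It also names the screening tool: "Suicidal ideation will be assessed during the trial each time the PHQ-9 depression self-report questionnaire is completed". A total score of 10 or more is passed to the radiation oncologist and the study psychiatrist. Ideation that is either marked on the form or volunteered counts as a serious adverse event.

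On the event window, Section 6.2 states: "All toxicities or adverse events occurring between the start of treatment and 30 days following the end of treatment will be recorded". Section 6.3.1 uses the same 30 days for serious events.

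The intervention-phase calendar in Section 9 marks the PHQ-9 at weeks 0 and 5, and the row "Adverse Events assessment" at weeks 1 and 5. Week 9 carries the FACIT fatigue subscale, a review of health status and life events, and the exit form.

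**The concern.** The plan cites late psychiatric events as a known feature of the injectable drug, promises systematic screening, and defines a window that runs a month past the last dose. It then schedules neither of its two detection instruments inside that month. The only scheduled contact there, at week 9, has one safety item, and the protocol does not say what that item asks.

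What is at stake is patient safety and the strength of the safety statement. A mild depression at week 5 that later worsens, or ideation that first appears off drug, would surface only by volunteered report or by chance. A later statement that no late psychiatric events occurred would then rest largely on passive reporting. The efficacy comparison is not affected.

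**Working it through.** No sample size, power or error rate enters here. The check compares the schedule with the text and then does interval arithmetic, counting day 0 as the start of dosing.

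**Is a PHQ-9 or adverse-event assessment scheduled after dosing?**

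| Item | Week 0 | Week 1 | Week 5 | Week 9 |
|---|---|---|---|---|
| FACIT fatigue subscale | X | X | X | X |
| PHQ-9 | X | | X | |
| Adverse-event assessment | | X | X | |
| Health status and life events | | | | X |

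The FACIT row is filled in all four columns, which confirms how the columns are read. Off drug there are 0 scheduled PHQ-9s and 0 scheduled adverse-event assessments.

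**Does anything else fill the gap?**
- *Monitoring-phase PHQ-9.* All three monitoring calendars repeat it four weeks after radiotherapy; the partial-breast footnote has it "then once while obtaining the final monitoring FACIT 4 weeks after end of RT". But by Section 5.3, "The monitoring phase terminates either at entrance into the intervention phase of the study", so randomised patients leave that schedule.
- *Other questionnaires.* FACT-B asks about sadness and GAD-7 about anxiety, but both are marked at weeks 0 and 5 only. Of the instruments reproduced, only the PHQ-9 has a suicidality item.
- *Adverse-event form.* The SAFTEE as printed has no item on depression or suicidal thoughts.
- *Week-9 health review.* It is not described anywhere, and the visit breakdown in Section 5.3 stops at week 5.
- *Extended follow-up in Section 5.6.* It applies to participants already removed for an adverse event, so it does not detect new ones.

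**How long is the unscreened off-drug period?** Inputs: dosing ends on day 35 (5 weeks); visits are ±7 days; the event window is the last dose plus 30 days.
- Nominal: the window closes on day 35 + 30 = 65; gap 65 − 35 = 30 days.
- Early week-5 visit with dosing ending there: 28 + 30 = 58; gap 58 − 28 = 30 days.
- Late PHQ-9 on day 42 after dosing ended on day 35: gap 65 − 42 = 23 days.

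**What would a week-9 PHQ-9 cover?** The form asks about the last 2 weeks (14 days). Dosing ends on day 35 and the window closes on day 65:

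| Week-9 visit | Look-back inside window | Off-drug days before it | Days after it |
|---|---|---|---|
| Day 56 | days 42–56: 14 | 42 − 35 = 7 | 65 − 56 = 9 |
| Day 63 | days 49–63: 14 | 49 − 35 = 14 | 65 − 63 = 2 |
| Day 70 | days 56–65: 9 | 56 − 35 = 21 | 0 |

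Each row sums to 30.

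**How many cases might be missed?** This cannot be estimated. The listed rate of under 1% gives fewer than 150 × 0.01 = 1.5 events in the naltrexone arm over the whole trial. The documents give no share arising after discontinuation.

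**The case against.** The strongest reply has four parts.

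- *No promise is broken.* The commitment in Section 6.1 names no visit, and Section 5.7 ties ideation screening to whenever the PHQ-9 is completed. This is fair as a reading of the words. But Section 5.6 follows randomised patients to four weeks after treatment, and the commitment comes directly after a description of post-discontinuation events. A schedule that stops at the last dose does not answer that description.
- *The risk transfers poorly.* The signal comes from the depot injection, for which Section 7.1.1 gives half-lives of 5–10 days, against 4 hours for oral naltrexone and 13 hours for its main metabolite. Ideation was not seen with oral drug, and Section 3.4 excludes major depression and suicidal ideation at entry. The late events cited arose in depressions that began on drug, which the week-5 PHQ-9 can catch. All of this stands and lowers the probability. What remains is a depression below the threshold at week 5 that worsens, or ideation that appears later.
- *Week 9 is not empty.* The health review sits under the safety heading of the calendar, and the schema assigns that visit to a nurse. It may well elicit general adverse events. It is not shown to be a standardised self-report instrument, or to ask about mood.
- *The appendices may be incomplete as supplied.* Further SAFTEE pages or a form for the health review cannot be ruled out, so the statement about SAFTEE applies to the form as printed. Neither possibility puts a PHQ-9 or an adverse-event assessment in the week-9 column.

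**Conclusion.** The concern holds. Between the end of dosing and the close of the 30-day event window, the plan schedules no depression or ideation screen and no adverse-event assessment. Nominally 30 off-drug days are unscreened, or 23 if the week-5 PHQ-9 is done a week late after dosing stopped on time. This rests on the intervention calendar as printed, on five weeks of dosing, and on the undefined week-9 review not being a structured mood screen.

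The event is grave but improbable, the number of missed cases cannot be estimated, and the primary analysis is untouched. The change should be made because it is nearly free; its practical priority is modest.

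**What to change.** Mark the PHQ-9 and the adverse-event assessment in the existing week-9 column of the intervention calendar. Both are needed, because the printed SAFTEE does not cover depression or ideation. Handle PHQ-9 results under the algorithm already in Section 5.7. Report PHQ-9 item 9 and the total score by arm at weeks 5 and 9 for everyone who took a dose; with so few events expected, this is descriptive. It would also help to state what the week-9 health review asks.

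The cost is a calendar amendment. Section 10.1 puts the PHQ-9 at 3 minutes, so 300 × 3 / 60 = 15 hours of patient time if all attend, scored by the existing coordinator. The adverse-event form comes on top; the plan gives no time for it, but it already fits the 15-minute week-1 visit, and week 9 is also allotted 15 minutes.

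The downsides are slightly more burden and a few extra same-day referrals. Nominally the first 14 days off drug (7 to 21 across the visit window) would still depend on volunteered reports unless symptoms persist into the look-back period.
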